1. Determine if our EMA measures of behavioral mechanisms have high response rates (> 90%) and are ready for R33 use.
2. Determine if there is preliminary evidence that the MBI intervention impacts our hypothesized mechanisms of action and that the proposed mechanisms predict improved dietary adherence.
3. Assess feasibility and acceptability of two intensities of maintenance (monthly group meetings alone or supplemented by individualized attention) to ensure they are ready for R33 testing.

R33 Specific Aims: We will randomize 120 persons with diabetes in a 1:2 ratio to the Ed (n=40) vs. Ed+MBI (n=80) arms and follow them for 12 months. After the 12-week intervention, we will observe participant for 8 weeks and then re-randomize them using an adaptive intervention design to receive further observation, light maintenance training, or intensive maintenance training, depending on level of adherence achieved during the observation period. We will address the following specific aims:

1. Test whether our proposed behavioral mechanisms (decreased eating in response to cravings or difficult emotions) predict dietary adherence.
2. Test the hypothesis that the Ed+MBI arm will have better dietary adherence than the Ed arm.
3. Compare randomized arms in the adaptive maintenance intervention design to optimize maintenance phase dosing in future trials.
4. Obtain preliminary assessment of intervention effects on clinical outcomes

Design and Outcomes

This is a two-phase study. Both phases will use a randomized, controlled trial design. After pilot testing in the first phase, the second phase will include employing an adaptive intervention design in the post-treatment phase to test optimization of the maintenance intervention (i.e. assigning maintenance intensity/dose based on how a participant is doing).

Interventions and Duration

Participants will attend 12-weekly study intervention classes based on their random assignment: either Education alone (Ed) or Education+Mindfulness (Ed+MBI). Both groups will learn and follow a CR diet, and will participate in maintenance phase activities. If assigned to Ed+MBI, they will also learn and practice mindfulness-based skills.

Sample Size and Population

Target sample size: 180 total (60 participants in the first/R61 phase, 120 in the second/R33 phase).

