9.2 Sample Size and Randomization

Target sample size: 180; 60 participants in the first/R61 phase. 120 in the second/R33 phase.

Our primary hypothesized mechanism is change in frequency of eating in response to cravings. Based on preliminary data, we expect that participants will report that on average, they have eaten in response to cravings on 50% of days on EMA measures at baseline (SD 11%). Our key concern is whether the Ed+MBI group has a significant decrease in days of eating in response to cravings. With N=30 persons in each arm, we will be able to detect a statistically significant decrease with 80% power (alpha=.05), if the group experiences eating in response to cravings on 44% of days or less. We will also test whether there are differences in decreases in cravings between groups.

Based on typical diet interventions for obese persons, we estimate that this will decrease to 30% of days in the Ed group, and 20% of days in the Ed+MBI group, for a mean difference of 10% (SD of 11%). With 30 people in each arm, this will provide us with a power of 80% to detect a statistically significant difference, using a two-tailed test, alpha=.05. For this phase, in which we are screening for evidence of effect on the proposed mechanism, we believe that a one-sided test, corresponding the hypothesis that the Ed+MBI group will have a greater effect on craving related eating than Ed alone, we will have 88% power. Note that we are not accounting for potential drop-outs in the analysis. We

anticipate that almost everyone will get through at least 4 weeks of intervention, which will provide initial data that can be used on all participants. In our pilot study of persons with T2DM and carbohydrate restricted diets, 94% completed the full 13 session program. Even if there is 20% dropout with no usable data, we will have 80% power to detect a statistically significant difference between groups in craving related eating, using a one-sided test.

Though of lesser concern at this early stage, we aim to test whether our hypothesized mechanisms are correlated with dietary adherence measures and will use linear regression. Using our overall sample of N=60, we will have greater than 80% power to detect a significant correlation if the true correlation coefficient (r) is .43 or greater. If we look just at the Ed+MBI group, we will have 80% power to detect a significant correlation if the true correlation coefficient (r) is .53 or greater.

Treatment Assignment Procedures

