For each of these measures, our primary analysis will be comparison of changes from baseline to follow-up time points between groups (see overall analysis approach above). We will also assess changes from baseline to follow-up within each group to help assess the potential effect of each intervention arm on these measures. We will also test for preliminary evidence that each of these proposed mechanisms is associated with dietary adherence. Dietary adherence will be measured two ways: (1) proportion of blood ketone measures $\geq 0.3\text{mmol/L}$; (2) proportion of kcal from carbohydrate, using 24-hour diet recall. Each of our mechanism measures are continuous variables. We will therefore assess correlations between each of the mechanism measures and the dietary adherence measures, using linear regression. Finally, we will perform initial analysis of whether there are differences in two important clinical outcomes between intervention groups: HbA1c (to examine glycemic control) and weight. These clinical outcomes should result from our intermediate behavioral outcome of improved dietary adherence. We do not expect to have adequate sample-size in either phase of this study to address this question, but believe that preliminary assessment of these outcomes should be performed in case there are dramatic differences between groups even with limited sample size.

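### The mechanism–adherence regression names no arm term, so Ed+MBI effects on both variables can induce a pooled association with no link within arms

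*Combined protocol and SAP*

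**What the plan says.** Section 9.6 states the aim: "We will also test for preliminary evidence that each of these proposed mechanisms is associated with dietary adherence". Linear regression is the method, and the plan is to "assess correlations between each of the mechanism measures and the dietary adherence measures". Adherence is measured in two ways: the share of blood ketone readings at or above 0.3 mmol/L, and the share of energy from carbohydrate on 24-hour recall. No covariate is listed for these regressions. Multiple regression is named in Section 9.6 only for comparing groups.

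The analysis set comes from Section 9.2: "Using our overall sample of N=60, we will have greater than 80% power to detect a significant correlation". The true r assumed there is at least .43. This is power for a simple correlation with both arms pooled. The next sentence gives a second version: "If we look just at the Ed+MBI group, we will have 80% power to detect a significant correlation", at r = .53. Section 9.6 does not say which version is the main one.

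For R33, Aim 1 in the Précis begins "Test whether our proposed behavioral mechanisms" and asks whether they predict adherence. The documents give no model for that aim, and no mediation or arm-adjusted model for either phase.

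**The concern.** The trial's own hypotheses make arm a common cause. Section 9.2 expects Ed+MBI to bring craving-related eating to 20% of days against 30% in Ed. Section 1.2 and R33 Aim 2 expect better adherence under Ed+MBI. The plan also describes routes from arm to adherence that need not pass through cravings. Section 5.2 gives Ed+MBI a one-hour mindfulness session before each weekly diet session of 1 to 1.25 hours, plus an app. Section 2.2 offers stress management as a route of its own.

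If Ed+MBI moves both variables, the arm means separate on both axes and the pooled data correlate, even when participants within an arm show no relation. Such a correlation repeats the two between-arm differences and adds nothing about mechanism. It could still be read as support for the second half of R61 Aim 2 and for R33 Aim 1, in a study whose stated purpose is to test mechanisms.

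**Working it through.** **The plan's own figures (Section 9.2).** Fisher z, two-sided 5% (assumed; no sidedness is given for the correlation): power = Φ(atanh(r)·√(n−3) − 1.96).
- n = 60, r = .43: Φ(0.460 × 7.550 − 1.96) = Φ(1.51) = 93.5%. The claim of more than 80% is true; the 80% point is r = .355.
- n = 30, r = .53: Φ(0.590 × 5.196 − 1.96) = Φ(1.11) = 86.6%, against a stated 80%; the 80% point is r = .492.

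Both stated figures are conservative, so power is not the problem.

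**Inputs for the arm-induced correlation.**
- Arm effect on craving-related eating: d1 = 10/11 = 0.91 SD (Section 9.2).
- Arm effect on adherence: not given in the documents. Assumed d2 = 0.2 to 0.91 SD.
- Allocation: 30 + 30 in R61; 40 + 80 in R33.
- Within-arm correlation: zero.

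**Formula.** With q the Ed+MBI share and v = q(1−q), the size of the pooled correlation is |r| = v·d1·d2 / √[(1 + v·d1²)(1 + v·d2²)].
- R61, v = 0.25, d2 = 0.91: 0.2066 / 1.2066 = .171.
- R33, v = 2/9, d2 = 0.91: 0.1837 / 1.1837 = .155.

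**Rejection rates.** Simulation with 20,000 trials per setting, normal data, two-sided 5%, d1 = 0.91:

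| Adherence effect d2 (assumed) | R61 \|r\| | R61, no arm term | R33 \|r\| | R33, no arm term | With arm term |
|---|---|---|---|---|---|
| 0 | 0 | 5% | 0 | 5% | 5% |
| 0.2 | .04 | 6% | .04 | 7% | 5% |
| 0.5 | .10 | 12% | .09 | 17% | 5% |
| 0.8 | .15 | 22% | .14 | 33% | 5% |
| 0.91 | .17 | 26% | .155 | 40% | 5% |

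Check by Fisher z on the 0.91 row: R61, Φ(0.173 × 7.550 − 1.96) = Φ(−0.66) ≈ 26%; R33, Φ(0.1565 × 10.817 − 1.96) = Φ(−0.27) ≈ 39%. Both agree with the simulation. The induced r hardly differs between phases; the R33 rate is higher because N is larger.

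**Sensitivity to d1.** With SD 11 and 30 per arm, the group comparison has Φ(0.909 × √15 − 1.96) = 94% power two-sided and 97% one-sided, not the stated 80% and 88%. The stated values fit an SD of about 13.5 to 14, so d1 = 10/14 to 10/13.5 = 0.71 to 0.74. At d1 = 0.73 the rates are 10% (R61) and 12.5% (R33) for d2 = 0.5, and 19% and 29% for d2 = 0.91.

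**Power with arm in the model.** At N = 60 and partial r = .43: Φ(0.460 × √56 − 1.96) = 93.1%, against 93.5% unadjusted. The r detectable with 80% power moves from .355 to .358.

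**The case against.** Several counter-arguments stand in part.

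- **The plan does not rule out adjustment.** A reader might infer a decision to leave arm out. The documents are silent: linear regression is named and covariates are neither listed nor excluded. However, a power statement for a simple pooled correlation points to an unadjusted analysis.
- **A within-arm version is mentioned.** The Ed+MBI-only correlation cannot be confounded by arm. It mitigates the gap but does not close it, because it is worded as an option and Section 9.6 does not adopt it.
- **The upper rates are not the plan's.** A reader might take 26% and 40% as following from planned effects on both variables. Only the craving effect is planned; the adherence effect is an assumption, and at 0.2 SD the inflation almost vanishes.
- **The induced correlation is modest.** A reader might infer that an MBI effect on both variables would produce a mechanism finding by itself. In R61, |r| of .04 to .17 lies below the significance cut-off of about .254 at N = 60, so in these scenarios 74% or more of R61 trials would show nothing significant.
- **The pooled association is real.** Section 9.6 tests association, and rejecting is correct for that null. The error lies in reading the result as evidence of mechanism. An arm term does not make that reading causal either, since motivation, for example, could drive both variables within an arm.
- **R61 gives this analysis low priority.** Section 9.6 calls the evidence preliminary and Section 9.2 ranks it below the group comparison at that stage. R33 Aim 1 carries no such label, but applying the Section 9.6 model to it is an inference.

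**Conclusion.** The concern holds as a gap in specification with a nearly free remedy. The pooled mechanism–adherence regression has no stated arm term, and the trial's own hypotheses supply the conditions under which that matters. With the planned craving effect of 0.91 SD, an assumed adherence effect of 0.2 to 0.91 SD and no within-arm link, the test rejects in about 6% to 26% of R61 trials. The R33 range is about 7% to 40%, conditional on the same model being used for R33 Aim 1. The rate is about 5% with arm included. It also stays at 5% without the arm term if Ed+MBI affects only one of the two variables, and the inflation is smaller at a craving effect near 0.73 SD.

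The documents do not support the stronger conclusions that the plan rejects adjustment, that a spurious association is the likely result in R61, or that adjusting for arm would establish the mechanism.

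**What to change.** In Section 9.6, state that the mechanism–adherence regressions in both phases include randomised arm as a covariate, and that the pooled unadjusted correlation is descriptive only. Describe the adjusted result as an association, since arm adjustment leaves other confounding of a non-randomised mechanism in place.

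The cost is one sentence, one degree of freedom and about 0.4 percentage points of power at r = .43 with N = 60. No new data are needed.

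Using earlier change in the mechanism to predict later adherence, and adding the baseline value and BMI stratum, are optional. They may sharpen interpretation or precision, but they do not address confounding by arm and are not needed for this correction.

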10. DATA COLLECTION AND QUALITY ASSURANCE

10.1 Data Collection Forms

Data will be collected by trained research assistants and study coordinators, using paper forms, as well as via online questionnaires using *Qualtrics*. All surveys and forms will be de-identified and coded with a unique subject number that will not contain personally identifiable information, such as subject initials or birthdates.

10.2 Data Management

The investigators are responsible for ensuring the accuracy, completeness, legibility, and timeliness of the data reported. All source documents will be completed in a neat, legible manner to ensure accurate interpretation of data. The investigators will maintain adequate case histories of study subjects, including accurate case report forms (CRFs), and source documentation.

Data collection and accurate documentation are the responsibility of the study staff under the supervision of the investigator. All source documents and laboratory reports will be reviewed by the study team and data entry staff, who will ensure that they are accurate and complete.

This study will use a Salesforce database. The database will be secured with password protection. The statistician will receive only coded information that is entered into the database under those identification numbers. Electronic communication with outside collaborators will involve only unidentifiable information. The database incorporates an electronic audit trail to show change(s) to data after original entry including the date/time and user making the change. Paper data collection forms will be used to collect a limited amount of data (e.g. health history and medications, weight), which will be entered into the Salesforce database after undergoing systematic review for

completeness, accuracy, and adherence to study protocols.

10.3 Quality Assurance

10.3.1 Training

All study staff will complete CITI human subjects training. This will be tracked and reviewed by the Project Director yearly or more frequently, with submission of each IRB modification or renewal (i.e. at least yearly). Study staff will also receive training from [name] on all study screening, enrollment, and assessment procedures, including data collection review and entry procedures. Trainings will incorporate both didactics as well as observation and modeling of appropriate procedures and conduct.

10.3.3 Metrics

Much of our data will be electronically and automatically captured (e.g. lab results), but we plan several steps to ensure data quality. EMA data will be reviewed on a weekly basis and questionable responses will be clarified with participants. For Qualtrics questionnaires, we will utilize range checks and other automated steps to prevent or check unusual responses; programming will be performed to require responses to key data elements. Lab results will be reviewed for clinical reasons before providing to participants, and unexpected values will be followed-up to ensure accuracy. The accuracy of hand-entered data will be checked via automatic checks for out-of-range values.

QA review and data verification will be performed by someone other than the individual originally collecting the data, or by double-data entry. We will review data at least monthly in order to take corrective action as needed for any trends in errors. We will use our study database to plan upcoming follow-up visits and ensure that these are appropriately scheduled. The database will also be used to identify any visits that are at risk of being overdue so that follow-up steps can be taken. A statement reflecting the results of the ongoing data review will be incorporated into the Annual Report for the Independent Safety Monitor(s).

10.3.4 Protocol Deviations

Protocol deviations will be captured by regular review of cases during the enrollment process by [name] to ensure that eligibility criteria are met. Key points of review include post-consent visit and baseline lab completion as well as before randomization. Checks will also be programmed into Salesforce to ensure that enrollees have completed necessary steps to enrollment. Deviations in data collection procedures will be captured via the following standard procedure: after each participant visit, the study staff member who conducted the visit will review the folder and data collection forms. A second review will be done by another staff member who wasn't involved in the data collection before data entry. Any discrepancies or potential problems will be documented and reviewed with [name] (or, over time and with training and supervision, with one of the lead study coordinators). [name] will periodically spot-check random participant folders to ensure compliance with procedures.

10.3.5 Monitoring

Protocol compliance and monitoring will be done via review of records and forms after each participant visit before data entry. Review will be done by a study staff member who was not involved in the data collection for that participant, and any discrepancies or potential problems will be reviewed by the [name] (Project Director). [name] will periodically spot-check random data collection forms to ensure compliance with procedures.

11. PARTICIPANT RIGHTS AND CONFIDENTIALITY

11.1 Institutional Review Board (IRB) Review

The protocol and the informed consent document (Appendix A) and any subsequent modifications will be reviewed and approved by the IRB or ethics committee responsible for oversight of the study.

11.2 Informed Consent Forms

A signed consent form will be obtained from each participant, using IRB-approved consent forms and procedures. The consent form will describe the purpose of the study, the procedures to be followed, and the risk and benefits of participation. A copy will be given to each participant and this fact will be documented in the participant record.

11.3 Participant Confidentiality

Participants will be assigned unique, coded, confidential identifiers (code numbers), which will be used to label all data forms, data entries and biological specimens, including LabCorp lab slips and results. Identifiable information, such as name, will not appear on these materials. The key linking the subject's identity to their unique coded identifier will be kept in a confidential manner in a database on a secure UCSF server, with access only by the principal investigator and the research staff. No names or individual identities will be used in publications resulting from the study. Physical records will be kept in an area accessible only to research staff. Research data will be stored on a secure, HIPAA-compliant server and drive with monitored and controlled access for study staff and investigators. The web-based survey will be hosted on secure servers. In addition, participants will enter only a study ID number, thus no identifying information will be associated with their questionnaire data. Online data collection avoids or minimizes the transfer of personally identifiable information, and uses industry best practices for protection of data. On the ERN forums, users are identified by self-selected screen names. Other users cannot see their email address or other identifying information. Participants must use an email address to register to use the ERN app. Participants will be told that if they choose, they can use an anonymous email address that is not connected to their identity for this process, and staff will offer to assist them in acquiring such an address if they wish. If they choose to do this, then the risk of privacy loss resulting from a breach in Claritas's security is reduced.

11.4 Study Discontinuation

The study may be discontinued at any time by the IRB, the NCCIH, the OHRP, or other government agencies as part of their duties to ensure that research participants are protected.

13. PUBLICATION OF RESEARCH FINDINGS

Conference abstracts and manuscript will be made available for review by study co-investigators included on the publication prior to submission.

15. SUPPLEMENTS/APPENDICES

- i. Consent form
